## 1.5 MODIFICATIONS TO THE STATISTICAL SECTION OF THE PROTOCOL

This section summarizes major changes to the protocol statistical section with emphasis on changes after study start (after the first patient was enrolled).

A few modifications are made in the statistical section in the following amendments.

### *Amendment 1*

The following cut-offs for age group and BMI group defined in the protocol:

- Age group (<45, ≥45 and < 65, ≥65 years old)
- BMI group (< 25, ≥25 kg/m^2)

were changed in Protocol Amendment 1 to:

- Age group (< 65, ≥65 and <75, ≥75 years old)
- BMI group (<25, ≥25 and <30, ≥30 kg/m^2)

### *Amendment 3*

- Updated the description of the study endpoints and statistical methodology for clarification purposes. The intent of the statistical analysis plan established in the original protocol is not changed.
- Incorporate the Rheumatoid Arthritis-Work Productivity Survey (WPS-RA) into the protocol for patients that completed the EFC10832 study. The WPS-RA is added into the LTS11210 study because the WPS-RA was included in the EFC10832
- Added x-ray data summary

### *Amendment 8*

- Added: Data analysis results for patients who roll over from EFC13752 will be presented separately as sarilumab is administered as monotherapy in the EFC13752 and these patients will continue to be on sarilumab monotherapy in LTS11210
- Updated analysis treatment groups: The safety analyses will be presented by original actual treatment groups in the respective previous studies (placebo, 150 mg q2w, 200 mg q2w, other sarilumab, and active control treatment groups) as well as overall in LTS11210, based on the reported adverse events, clinical laboratory evaluations, vital signs, and 12-lead ECGs
- Updated analysis treatment groups: The efficacy analyses will be done descriptively on the safety population by the originally randomized treatment groups as assigned in the respective previous studies (placebo, 150 mg q2w, 200 mg q2w, other sarilumab, and active control treatment groups) as well as overall and by visit in observed case, as appropriate

- Add: Radiographic progression of the mTSS is defined as a change from baseline in the mTSS  $>0$ . A change from baseline in the mTSS of less than or equal to zero is considered as no progression. The event of missing a change from baseline in the mTSS will be considered as progression. Summary of incidence of radiographic progression of mTSS will be provided
- Deleted X-ray assessment at Week 192 as the time point is very close to EOT visit. X-rays performed at EOT will serve as source to provide X-ray data after 5 years of treatment with sarilumab.
- Changed Section 13.8 title “Database Lock” as “Interim Analysis” with sentence modification.

### ***Amendment 9***

- Adjust timepoints up to Week 264 for efficacy endpoints (except DAS28 and EULAR) and health economic variables
- The timepoints are up to Week 516 for DAS28 and EULAR endpoints
- Updated analysis treatment groups for patients from EFC11072, ACT11575, EFC10832 and SFY13370 with sarilumab + DMARD therapy in the initial and current studies , and for patients from EFC13752 with sarilumab monotherapy in the initial and current studies, per previous SAP version 2
- Clearly state serum concentrations of bound Sarilumab are not analyzed per sponsor’s decision after EFC11072 study
- Clearly state 3 campaigns of x-ray data (2 year data up to Week 48, 3 year data up to Week 96, and 5 year data up to Week 192 in LTS11210)
- Add the PFS-S sub-study (see Protocol Amendment 9 Appendix R)

## **1.6 STATISTICAL MODIFICATIONS MADE IN THE STATISTICAL ANALYSIS PLAN**

The statistical analysis plan (SAP) Versions 1 and 2 were based on the original protocol dated 16 Febr2010, and Protocol Amendments 1-8, respectively. The current SAP is modified per Protocol Amendment 9 with the modification mentioned in [Section 1.5](#)

## 2 STATISTICAL AND ANALYTICAL PROCEDURES

Below are general rules for the analysis procedure.

For patients from EFC11072, ACT11575, EFC10832 and SFY13370 with sarilumab + DMARD therapy in the initial and current studies, all analyses will be performed based on previous treatment prior to enrollment into LTS11210 (placebo, sarilumab 150 mg q2w, sarilumab 200 mg q2w, other sarilumab (non-selected) doses, and active control treatment) as well as overall in LTS11210, unless otherwise specified. Interim analyses may be performed based on overall sarilumab +DMARD therapy only.

For patients from EFC13752 with sarilumab monotherapy in the initial and current studies, all analyses will be performed based on previous treatment prior to enrollment into LTS11210 (sarilumab 150 mg q2w, sarilumab 200 mg q2w) as well as overall in LTS11210, unless otherwise specified. Interim analyses may be performed based on overall sarilumab monotherapy only.

Data analysis results will be presented by sarilumab +DMARD therapy and sarilumab monotherapy in LTS11210 separately. All analyses will be performed in observed cases unless otherwise specified.

Data analyses for the PFS-S sub-study will be described in [Appendix K](#).

### 2.1 ANALYSIS ENDPOINTS

#### 2.1.1 Demographic and baseline characteristics

For patients who roll over to LTS11210, new demographic data are collected in LTS11210, but some baseline characteristic information (such as height, time since diagnosis of RA, rheumatoid factor and prior biologic use) is not collected in LTS11210. This missed information will be captured from the previous study databases.

All baseline safety and efficacy parameters (apart from the ones listed below) are presented along with the on-treatment summary statistics in the safety and efficacy sections ([Section 2.4.4](#) and [Section 2.4.5](#)).

#### *Demographic characteristics*

The following demographic characteristics will be summarized:

- Gender (Male, Female)
- Race (Caucasian/white, Black, Asian/Oriental, other)
- Ethnicity (Hispanic, Not Hispanic)
- Region (Region1:Western countries, Region2:South America, Region3:Rest of the World)

- Age (years)
- Age group (< 65, ≥65 and <75, ≥75 years)
- Weight (kg)
- Height (cm)
- Body mass index (BMI, kg/m^2)
- BMI group (<25, ≥25 and < 30, ≥30 kg/m^2).

### ***Medical or surgical history***

The medical and surgical history data were collected in the previous studies.

This information will be coded to a “Lower Level Term (LLT)”, “Preferred Term (PT)”, “High Level Term (HLT)”, “High Level Group Term (HLGT)”, and associated primary “System Organ Class (SOC)” using the version of MedDRA currently in effect at sanofi at the time of database lock.

### ***Disease characteristics at baseline***

The following baseline disease characteristics will be summarized:

- Time since diagnosis of RA (years)
- Rheumatoid factor (Positive: ≥1 IU/mL, negative: <1 IU/mL)
- Prior biologic DMARD use for RA
- Smoking history
- Alcohol use

In addition, the summary of baseline values for clinical signs and symptoms and quality of life assessments will be presented in the summary tables for these data.

Any technical details related to computation, dates, imputation for missing dates are described in [Section 2.5](#).

### **2.1.2 Prior or concomitant medications**

All medications taken at any time during LTS11210 period, from the enrollment to the end of the follow-up period, including those ongoing at study start, are to be reported in the CRF pages.

All medications will be coded using the World Health Organization-Drug Dictionary (WHO-DD) using version currently in effect at sanofi at the time of database lock.

Concomitant medications are any treatments received by the patient concomitantly to the/any IMP, from the first IMP intake in LTS11210 to the end of the follow-up period.

Prior medications are those the patient used prior to first IMP intake in LTS11210. Prior medications can be discontinued before first dosing or can be ongoing during treatment phase. The data before enrollment were reported in the previous study reports. However the data from enrollment up to the time of first IMP intake will be reported in LTS11210 database.

Any technical details related to computation, dates, imputation for missing dates are described in [Section 2.5](#).

### **2.1.3 Safety endpoints**

The primary endpoint is the incidence of adverse events. The safety analysis will be based on the reported adverse events (AEs) and other safety information, such as clinical laboratory data, vital signs and ECG.

#### ***Observation period***

The observation period will be divided into 4 epochs:

- The SCREENING epoch is defined as beginning with the last visit in the previous studies to the first dose of IMP in LTS11210
- The TREATMENT epoch is defined as the time from first dose of IMP in LTS11210 to last dose of IMP + 13 days (6 days for patients receiving weekly injections only)
- The FOLLOW-UP epoch is defined as the time from the end of TREATMENT epoch to last dose of IMP + 60 days
- The POST-STUDY epoch is defined as the time after the last dose of IMP + 60 days

The rationale of having “last dose of IMP + 60 days” as the end of follow-up epoch is to capture the events observed within an approximately 5 half-lives of the last IMP. The treatment-emergent AE (TEAE) period will include both TREATMENT and FOLLOW-UP epochs.

Please note: Not all the patients will have all 4 epochs. For example, if a patient died on the 7th day after the last dose of IMP, his/her TREATMENT epoch will be from the first dose of IMP to his/her death date and will have no FOLLOW-UP or POST-STUDY epoch; if a patient had his last visit (i.e. follow-up visit 29) on the 50th day after the last dose of IMP and have no AE reported after this date, his/her FOLLOW-UP epoch will be ended on last dose of IMP+50 days and will have no POST-STUDY epoch.

#### **2.1.3.1 Adverse events variables**

Adverse event observation period

- Pre-treatment AEs are AEs that developed or worsened or became serious from the signed informed consent date up to first dose of IMP in LTS11210. The ongoing AEs from previous studies filled out on AE switch CRF pages are also considered as pre-treatment AEs

- TEAEs are AEs that developed or worsened or became serious during the TEAE period
- Post-study AEs are AEs that developed or worsened or became serious during the post-study period

All AEs (including SAEs and AESIs and ongoing AEs from previous studies filled out on AE switch CRF pages) will be coded to a “Lowest Level Term (LLT)”, “Preferred Term (PT)”, “High Level term (HLT)”, “High Group Level Term (HLGT)” and associated primary “System Organ Class (SOC)” using the version of MedDRA currently in effect at sanofi at the time of database lock.

The occurrence of AEs (including SAEs and AESIs and ongoing AEs from previous studies filled out on AE switch CRF pages) will be recorded from the time of signed informed consent until the end of the study.

***Adverse event of special interest (AESI)***

AESIs will be flagged in the database using search criteria. All AEs captured on the general AE form, the ALT increase form, the suspected infection event form, the diverticulitis or gastrointestinal ulceration form, or the neurological event form will be searched. The list of the AESIs with the search criteria are provided below:

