### **10.2.2 Demyelinating / Neurological events**

Any demyelinating event or significant, unexplained neurological symptom should be considered as an adverse event with prespecified monitoring (see [Section 10.5.4](#)). Refer to [Section 11.2](#) for demyelinating/neurological events requiring permanent treatment discontinuation.

Rarely, biologics have been associated with Progressive Multifocal Leukoencephalopathy (PML). The investigator should check any signs that might be suggestive of a PML at every visit: such as, but not limited to, unusual weakness, loss of coordination, changes in vision, difficulty speaking and sometimes personality changes. In case of suspicion of an event potentially related to a demyelinating event or significant, unexplained neurological symptom during the course of the study, the patient should be referred to a neurologist for a complete examination.

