- Lupus like syndrome
- Demyelinating events (including suspicion of PML) or significant unexplained neurological symptoms meeting seriousness criteria
- Gastrointestinal perforation
- Specific cardiovascular events and deaths (see [Section 10.2.10](#)):
  - Myocardial infarction
  - Stroke
  - Hospitalization due to unstable angina
  - Hospitalization due to heart failure
  - Hospitalization due to transient ischemic attack
  - Deaths (cardiovascular and noncardiovascular)

- Pregnancy:
  - Pregnancy occurring in a female patient included in the clinical study (as well as pregnancy occurring in a female partner of a male patient included in the study with IMP/NIMP) will be recorded as a pre-specified AE with immediate notification in all cases. It will be qualified as an SAE only if it fulfills the SAE criteria.
  - In the event of pregnancy in a female patient included in the trial, IMP should be discontinued.
  - The follow-up of the pregnancy in a female participant or in a female partner of a male participant will be mandatory until the outcome has been determined.
- Symptomatic Overdose with IMP/NIMP:
  - An overdose (accidental or intentional) with the IMP is an event suspected by the Investigator or spontaneously notified by the patient and defined as at least twice the dose of IMP during an interval of less than 11 days (NOTE: this definition was less than 6 days for patients on the initial weekly dosing regimen in the study). The circumstances (ie, accidental or intentional) should be clearly specified in the verbatim and symptoms, if any, entered on separate AE forms.
  - An overdose (accidental or intentional) with any NIMP (as defined in [Section 8.2](#)) is an event suspected by the Investigator or spontaneously notified by the patient and defined as at least twice of the intended dose within the intended therapeutic interval. The circumstances (ie, accidental or intentional) should be clearly specified in the verbatim and symptoms, if any, entered on separate adverse event forms.

In addition, the following AESIs/AEPs with immediate reporting must always be considered as medically important if not fulfilling any other seriousness criteria (see [Section 10.4](#)) and reported as serious adverse events.

- Systemic opportunistic infections
- Grade 4 neutropenia lasting for at least 5 days
- Anaphylaxis fulfilling the criteria in [Appendix O](#)

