- Demyelinating events (including suspicion of PML), or significant, unexplained neurological symptoms meeting seriousness criteria
- Gastrointestinal perforation
- Myocardial infarction
- Stroke
- Hospitalization due to unstable angina
- Hospitalization due to heart failure
- Hospitalization due to transient ischemic attack
- Deaths (cardiovascular and noncardiovascular)

For the following AEPM/AESI, the Sponsor **will not** require immediate notification; however if the event meets any seriousness criteria as per the Investigator's judgment, it should be reported as a SAE.

- Neutropenia grade 3 ( $<1000$  and  $\geq 500/\text{mm}^3$ ) without permanent treatment discontinuation (see [Section 10.2.5](#))
- Thrombocytopenia ( $<100\ 000/\text{mm}^3$ ) without permanent treatment discontinuation (see [Section 10.2.6](#))
- ALT elevation  $\geq 3$  x ULN without permanent treatment discontinuation (see [Section 10.2.4](#))
- Confirmed diverticulitis or gastrointestinal ulceration (see [Section 10.2.8](#))
- Significant unexplained neurological symptoms not meeting seriousness criteria (see [Section 10.2.2](#))
- Asymptomatic overdose (definition described above) with IMP/NIMP. The circumstances (ie, accidental or intentional) and the lack of symptoms (ie, asymptomatic) should be clearly specified in the verbatim.

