		• Systemic opportunistic infection	Yes	Yes	Yes
		• Grade 4 neutropenia lasting for at least 5 days	Yes	Yes	No
		• Anaphylaxis (defined in Appendix O , report as SAE)	Yes	Yes	No
		• Gastrointestinal perforation	Yes	Yes	Yes
		• Demyelinating events (including suspicion of PML) or significant, unexplained neurological symptoms meeting seriousness criteria	Yes	Yes	Yes
		• Specific cardiovascular events and deaths:	Yes	Yes	No b
		- Myocardial infarction			
		- Stroke			
		- Hospitalization due to unstable angina			
		- Hospitalization due to heart failure			
		- Hospitalization due to transient ischemic attack			
		- Deaths (cardiovascular and noncardiovascular)			
AESI WITHOUT immediate notification (non-SAE)	Routine	Neutropenia grade 3 (<1000 and ≥500 mm  ) without permanent treatment discontinuation	Yes	No	No
		Thrombocytopenia (<100,000/mm  ) without permanent treatment discontinuation	Yes	No	No
		ALT elevation ≥ 3 x ULN without permanent treatment discontinuation	Yes	No	Yes
		Confirmed diverticulitis or gastrointestinal ulceration	Yes	No	Yes
		Demyelinating events or significant, unexplained neurological symptoms not meeting seriousness criteria	Yes	No	Yes
		Asymptomatic overdose with IMP/NIMP	Yes	No	No
• Reminder: Safety Complementary Forms should be completed for all SAEs, AESIs with immediate notification, pregnancies, and symptomatic overdoses					
a This corresponds to "Drug exposure via parent data collection form" used by Global Pharmacovigilance and Epidemiology.					
b No specific form in CRF but a cardiovascular adjudication package needs to be submitted to the Cardiovascular adjudication committee.					

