### *Adverse events of special interest (AESI)*

AESIs will be flagged using search criteria. If available, a Standard MedDRA Query (SMQ) will be used to search (narrow search). If no SMQ is available, then a Sponsor defined search criteria will be used. The number and percentage of patients with treatment emergent AESIs will be summarized by AESI category and PT.

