**Table 1 - AESI and search criteria**

AESI flag	Searcha criteria
Leukopenia	SMQ: Haematopoietic leukopenia
Thrombocytopenia	SMQ: Haematopoietic thrombocytopenia
Infections (Opportunistic infections, Tuberculosis)	Primary SOC: Infections and infestations (CRF checkbox: Opportunistic infections; HLT Tuberculosis infections)
Hepatic disorders	SMQ : Drug-related hepatic disorders – comprehensive search
Diverticulitis/potential GI perforations b	SMQ: Gastrointestinal perforation and HLT: Diverticulum inflammations
GI ulcerations	SMQ: Gastrointestinal ulceration
Elevation in lipids	SMQ: Dyslipidemias
Anaphylaxis	SMQ: Anaphylactic reaction
Hypersensitivity	SMQ Hypersensitivity
Injection site reactions	HLT Injection site reactions
Malignancy	SMQ: Malignant or unspecified tumours Excluding non-melanoma skin cancer: SMQ Malignant or unspecified tumours excluding HLT of Skin neoplasms malignant and unspecified (excl melanoma)
Lupus-like syndrome	SMQ: Systemic lupus erythematosus
Demyelinating disorders	SMQ: Demyelination
Pregnancy c	CRF checkbox: Pregnancy
Overdose c	CRF checkbox: Symptomatic overdose

a All SMQs are narrow search  b These events will be further reviewed to identify cases of GI perforations  c Standard AESI applies to all Sanofi studies
	

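### SAP Table 1 has no search criterion for significant unexplained neurological symptoms, a protocol AESI, so events coded outside the narrow demyelination SMQ get no neurological AESI display

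*SAP*

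**What the plan says.** **Protocol.** Section 10.2.2 sets the class: "Any demyelinating event or significant, unexplained neurological symptom should be considered as an adverse event with prespecified monitoring". Section 10.5.4 places it in both reporting tiers. With immediate notification: "Demyelinating events (including suspicion of PML) or significant unexplained neurological symptoms meeting seriousness criteria". Without it: "Significant unexplained neurological symptoms not meeting seriousness criteria". Table 3 repeats the non-serious tier as "Demyelinating events or significant, unexplained neurological symptoms not meeting seriousness criteria" and marks a specific form as required in both tiers. Section 13.5.4.1 asks for the number and percentage of patients by AESI category and PT. The search uses a narrow SMQ where one exists, and otherwise: "If no SMQ is available, then a Sponsor defined search criteria will be used".

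**SAP.** Section 2.1.3.1 states that AESIs are flagged by search criteria. Besides the general AE page and the form for ALT elevations, its list of sources reads: "the suspected infection event form, the diverticulitis or gastrointestinal ulceration form, or the neurological event form will be searched". The criteria are those in Table 1. The only neurological row is Demyelinating disorders, defined as "SMQ: Demyelination", and a footnote makes every SMQ a narrow search. Some other rows use the case report form directly, for example "CRF checkbox: Symptomatic overdose". Section 2.4.4.1 limits the AESI summaries to events that meet the search criteria.

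**The concern.** The SAP names the neurological event form as a place to search, but appearing on that form does not set a flag. Only a Table 1 match does. An unexplained symptom, by its nature, has not been given a demyelinating diagnosis, so there is no reason to expect it to code into a narrow demyelination SMQ. Followed exactly, the plan leaves a protocol AESI out of the AESI analysis.

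Protocol section 4 says the study is meant to find late-onset events. The by-visit count of patients at risk and with events, given only for AESI categories, is the only adverse event count over time in SAP 2.4.4.1 and 2.4.4.2. Unexplained neurological symptoms would have no such table. If they are recorded under several different preferred terms, the SOC-to-PT tables would not bring them together as a class.

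**Working it through.** No arithmetic beyond counting applies, because safety is analysed descriptively and the point concerns search criteria. The check sets the protocol's AESI list against the SAP.

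**1. Flags.** SAP Table 1 has 15 flags. One is neurological (Demyelinating disorders). None covers unexplained neurological symptoms. Three draw on a CRF checkbox: opportunistic infections (within the Infections row), pregnancy and overdose.

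**2. Forms against flags.** SAP 2.1.3.1 names four event-specific forms besides the general AE form.

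| Form | Matching Table 1 row |
|---|---|
| ALT increase | Hepatic disorders |
| Suspected infection | Infections |
| Diverticulitis or GI ulceration | Diverticulitis/potential GI perforations; GI ulcerations |
| Neurological event | Demyelinating disorders only |

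Three of the four forms have a row for the class they are named after. The neurological form has a row for one of its two protocol classes.

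**3. Other routes in the SAP.** Sections 1.5 and 1.6 record no removal of this AESI, and protocol 10.4 says AESIs are added or removed by amendment. No other SAP rule flags the class. Some events may be caught elsewhere: an infectious cause under Infections, which is defined by SOC, and stroke or hospitalised TIA through cardiovascular adjudication. Protocol 10.5.1 asks investigators to report a diagnosis where possible, so the gap concerns mainly symptoms that stay unexplained.

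**4. What an unflagged event keeps and loses.** SAP 2.4.4.1 lists seven minimum displays per AESI category.

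| AESI display | Counterpart in the general tables? |
|---|---|
| Incidence by patient and by event | Yes (all TEAEs) |
| Serious | Yes (treatment-emergent SAEs) |
| Leading to discontinuation | Yes |
| Leading to death | Yes (SAP 2.4.4.2) |
| Possibly related | Yes (TEAEs by relationship) |
| Class overview | No |
| Class treatment-duration summary | No |

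Five of the seven have a SOC-to-PT counterpart and two do not. Two further items are lost:

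- the number at risk and number with events by visit, given only for AESI categories;
- for non-serious events, patients with an event per 100 patient-years, which SAP 2.4.4.1 limits to serious TEAEs and AESI types (formula in 2.5.1: 100 × n / Σtᵢ).

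Events per 100 patient-years remain, because 2.4.4.1 gives that rate for all TEAE summaries.

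**The case against.** The strongest reply is that a reporting AESI need not be an analysis AESI. Protocol 10.4 and 10.5.4 deal with monitoring and notification, and the statistical section names no categories. Table 1 is not a copy of the 10.5.4 list either, since it adds lipids, hypersensitivity, injection site reactions and malignancy. The immediate-notification entry and Table 3 join demyelinating events and unexplained symptoms in one line, and an SMQ is used for that line.

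This does not close the gap. Adding classes to Table 1 does not justify omitting a listed one. A demyelination SMQ does not cover unexplained symptoms merely because they share a line with demyelinating events, and the tier without immediate notification in 10.5.4 lists the symptoms alone.

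Several points do stand and limit the impact:

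- The general tables give patient counts at SOC and HLGT level as well as PT.
- All TEAEs are listed individually, and SAP 2.5.3 keeps imputed onset dates out of listings, which implies that reported dates appear there. Timing can therefore be read case by case; what is missing is a summary table.
- Serious cases reach the sponsor within 24 hours, and the DMC reviews specific adverse events, so signal detection does not rest on Table 1 alone.
- Unexplained is a diagnostic status and not a coding term. A term list would also pick up explained symptoms, so it is the weaker of the two remedies.

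**Conclusion.** The concern holds. SAP Table 1 covers one of the two neurological AESI classes in the protocol. The other has no criterion, although protocol 13.5.4.1 provides for a sponsor-defined search where no SMQ exists.

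The consequence is moderate and confined to presentation. The class loses its pooled overview, its treatment-duration summary and its by-visit count, and non-serious events lose the patient-based rate. No event disappears from the report, and the primary endpoint total does not change. The number of affected events cannot be stated: the documents give no event count and do not list the terms in the narrow demyelination SMQ. The conclusion assumes only that some events on the neurological form code outside that SMQ and under no other Table 1 row. It should be corrected before database lock, so that the grouping is not defined after the data are seen.

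**What to change.** Add one row to SAP Table 1: a neurological AESI defined as any event reported on the neurological event form, with the narrow demyelination SMQ shown as a subset. Apply to it the AESI displays of section 2.4.4.1, the by-visit table and the patients-with-event rate per 100 patient-years, with a breakdown by PT.

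The cost is one table row and one more set of standard outputs, from a form the SAP already searches. CRF-based flags already have precedent in Table 1. The form itself is not in the documents; if it cannot isolate these events, a sponsor-defined term list under protocol 13.5.4.1 is the fallback. The drawback is a mixed category that depends on investigator selection. The demyelination subset and the PT breakdown keep it readable.
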